11.9 Publication of Results

All manuscripts, abstracts, or other modes of presentation arising from the results of the study must be reviewed and approved in writing by the sponsor in advance of submission pursuant to the terms and conditions set forth in the executed Clinical Trial Agreement between the sponsor and the institution/investigator. The review is aimed at protecting the

sponsor's proprietary information existing either at the date of the commencement of the study or generated during the study.

The detailed obligations regarding the publication of any data, material results, or other information, generated or created in relation to the study shall be set out in the agreement between each investigator and the sponsor, as appropriate.

11.10 Disclosure and Confidentiality

The contents of this protocol and any amendments and results obtained during the study should be kept confidential by the investigator, the investigator's staff, and the IRB/IEC and will not be disclosed in whole or in part to others, or used for any purpose other than reviewing or performing the study, without the written consent of the sponsor. No data collected as part of this study will be used in any written work, including publications, without the written consent of the sponsor. These obligations of confidentiality and non-use shall in no way diminish such obligations as set forth in either the Confidentiality Agreement or Clinical Trial Agreement executed between the sponsor/ and the institution/investigator.

All persons assisting in the performance of this study must be bound by the obligations of confidentiality and non-use set forth in either the Confidentiality Agreement or Clinical Trial Agreement executed between the institution/investigator and the sponsor.

11.11 Discontinuation of Study

The sponsor reserves the right to discontinue the study for medical reasons or any other reason at any time. If a study is prematurely terminated or suspended, the sponsor will promptly inform the investigators/institutions and regulatory authorities of the termination or suspension and the reason(s) for the termination or suspension. The IRB will also be informed promptly and provided the reason(s) for the termination or suspension by the sponsor or by the investigator/institution, as specified by the applicable regulatory requirement(s).

The investigator reserves the right to discontinue the study should his/her judgment so dictate. If the investigator terminates or suspends a study without prior agreement of the sponsor, the investigator should inform the institution where applicable, and the investigator/institution should promptly inform the sponsor and the IRB and provide the sponsor and the IRB with a detailed written explanation of the termination or suspension. Study records must be retained as noted above.

11.12 Subject Insurance and Indemnity

The sponsor will provide insurance for any subjects participating in the study in accordance with all applicable laws and regulations.

12 APPENDICES

Appendix 1 Sponsor's Grading for Laboratory Values

Sponsor's Grading for Laboratory Values				
	Grade 1	Grade 2	Grade 3	Grade 4
BLOOD/BONE MARROW				
Hemoglobin	<LLN – 10.0 g/dL <LLN – 100 g/L <LLN – 6.2 mmol/L	<10.0 – 8.0 g/dL <100 – 80 g/L <6.2 – 4.9 mmol/L	<8.0 g/dL <80 g/L <4.9 mmol/L; transfusion indicated	life-threatening consequences; urgent intervention indicated
Leukocytes (total WBC)	<LLN – 3.0×10 ⁹ /L <LLN – 3000/mm ³	<3.0 – 2.0×10 ⁹ /L <3000 – 2000/mm ³	<2.0 – 1.0×10 ⁹ /L <2000 – 1000/mm ³	<1.0×10 ⁹ /L <1000/mm ³
Lymphocytes	<LLN – 800/mm ³ <LLN – 0.8×10 ⁹ /L	<800 – 500/mm ³ <0.8 – 0.5×10 ⁹ /L	<500 – 200/mm ³ <0.5 – 0.2×10 ⁹ /L	<200/mm ³ <0.2×10 ⁹ /L
Neutrophils	<LLN – 1.5×10 ⁹ /L <LLN – 1500/mm ³	<1.5 – 1.0×10 ⁹ /L <1500 – 1000/mm ³	<1.0 – 0.5×10 ⁹ /L <1000 – 500/mm ³	<0.5×10 ⁹ /L <500/mm ³
Platelets	<LLN – 75.0×10 ⁹ /L <LLN – 75,000/mm ³	<75.0 – 50.0×10 ⁹ /L <75,000 – 50,000/mm ³	<50.0 – 25.0×10 ⁹ /L <50,000 – 25,000/mm ³	<25.0×10 ⁹ /L <25,000/mm ³
METABOLIC/LABORATORY				
Albumin, serum- low (hypoalbuminemia)	<LLN – 3 g/dL <LLN – 30 g/L	<3 – 2 g/dL <30 – 20 g/L	<2 g/dL <20 g/L	life-threatening consequences; urgent intervention indicated
Alkaline phosphatase	>ULN – 3.0×ULN	>3.0 – 5.0×ULN	>5.0 – 20.0×ULN	>20.0×ULN
ALT	>ULN – 3.0×ULN	>3.0 – 5.0×ULN	>5.0 – 20.0×ULN	>20.0×ULN
AST	>ULN – 3.0×ULN	>3.0 – 5.0×ULN	>5.0 – 20.0×ULN	>20.0×ULN
Bilirubin (hyperbilirubinemia)	>ULN – 1.5×ULN	>1.5 – 3.0×ULN	>3.0 – 10.0×ULN	>10.0×ULN
Calcium, serum-low (hypocalcemia)	<LLN – 8.0 mg/dL <LLN – 2.0 mmol/L	<8.0 – 7.0 mg/dL <2.0 – 1.75 mmol/L	<7.0 – 6.0 mg/dL <1.75 – 1.5 mmol/L	<6.0 mg/dL <1.5 mmol/L
Calcium, serum-high (hypercalcemia)	>ULN – 11.5 mg/dL >ULN – 2.9 mmol/L	>11.5 – 12.5 mg/dL >2.9 – 3.1 mmol/L	>12.5 – 13.5 mg/dL >3.1 – 3.4 mmol/L	>13.5 mg/dL >3.4 mmol/L
Cholesterol, serum-high (hypercholesterolemia)	>ULN – 300 mg/dL >ULN – 7.75 mmol/L	>300 – 400 mg/dL >7.75 – 10.34 mmol/L	>400 – 500 mg/dL >10.34 – 12.92 mmol/L	>500 mg/dL >12.92 mmol/L
Creatinine	>ULN – 1.5×ULN	>1.5 – 3.0×ULN	>3.0 – 6.0×ULN	>6.0×ULN
GGT (γ-glutamyl transpeptidase)	>ULN – 3.0×ULN	>3.0 – 5.0×ULN	>5.0 – 20.0×ULN	>20.0×ULN
Glucose, serum-high (hyperglycemia)	Fasting glucose value: >ULN – 160 mg/dL >ULN – 8.9 mmol/L	Fasting glucose value: >160 – 250 mg/dL >8.9 – 13.9 mmol/L	>250 – 500 mg/dL; >13.9 – 27.8 mmol/L; hospitalization indicated	>500 mg/dL; >27.8 mmol/L; life-threatening consequences
Glucose, serum-low (hypoglycemia)	<LLN – 55 mg/dL <LLN – 3.0 mmol/L	<55 – 40 mg/dL <3.0 – 2.2 mmol/L	<40 – 30 mg/dL <2.2 – 1.7 mmol/L	<30 mg/dL <1.7 mmol/L life-threatening consequences; seizures

Sponsor's Grading for Laboratory Values				
	Grade 1	Grade 2	Grade 3	Grade 4
Phosphate, serum-low (hypophosphatemia)	<LLN – 2.5 mg/dL <LLN – 0.8 mmol/L	<2.5 – 2.0 mg/dL <0.8 – 0.6 mmol/L	<2.0 – 1.0 mg/dL <0.6 – 0.3 mmol/L	<1.0 mg/dL <0.3 mmol/L life-threatening consequences
Potassium, serum-high (hyperkalemia)	>ULN – 5.5 mmol/L	>5.5 – 6.0 mmol/L	>6.0 – 7.0 mmol/L hospitalization indicated	>7.0 mmol/L life-threatening consequences
Potassium, serum-low (hypokalemia)	<LLN – 3.0 mmol/L	<LLN – 3.0 mmol/L; symptomatic; intervention indicated	<3.0 – 2.5 mmol/L hospitalization indicated	<2.5 mmol/L life-threatening consequences
Sodium, serum-high (hypernatremia)	>ULN – 150 mmol/L	>150 – 155 mmol/L	>155 – 160 mmol/L hospitalization indicated	>160 mmol/L life-threatening consequences
Sodium, serum-low (hyponatremia)	<LLN – 130 mmol/L	N/A	<130 – 120 mmol/L	<120 mmol/L life-threatening consequences
Triglyceride, serum-high (hypertriglyceridemia)	150 – 300 mg/dL 1.71 – 3.42 mmol/L	>300 – 500 mg/dL >3.42 – 5.7 mmol/L	>500 – 1000 mg/dL >5.7 – 11.4 mmol/L	>1000 mg/dL >11.4 mmol/L life-threatening consequences
Uric acid, serum-high (hyperuricemia)	>ULN – 10 mg/dL ≤0.59 mmol/L without physiologic consequences	N/A	>ULN – 10 mg/dL ≤0.59 mmol/L with physiologic consequences	>10 mg/dL >0.59 mmol/L life-threatening consequences

ALT = alanine aminotransferase (serum glutamic pyruvic transaminase), AST = aspartate aminotransferase (serum glutamic oxaloacetic transaminase), GGT = γ -glutamyl transpeptidase, N/A = not applicable, LLN = lower limit of normal, ULN = upper limit of normal, WBC = white blood cell.

Based on Common Terminology Criteria for Adverse events (CTCAE) Version 4.0. Published: May 28, 2009 (v4.03: June 14, 2010).

Appendix 2 List of Prohibited Medications

If a medication is not presented in the list below, but does fit into a class of medications noted in the list, the medical monitor must be consulted to determine whether it is permitted.

Category	Medication
Anticholinergics (centrally-acting)	-
Anticonvulsants with known sedating effects	
 • Barbiturates • Benzodiazepines • GABA analogues • Hydantoins • Phenyltriazines
Antihistamines (centrally-acting H1, including over-the-counter)	
 • Diphenhydramine • Carbinoxamine • Doxylamine • Dimenhydrinate • Triprolidine • Brompheniramine • Chlorphenamine • Hydroxazine
Antihistamines with known sedating effects	Non-sedating, eg, Loratidine is not prohibited
Anxiolytics with known sedating effects	
 • Lorazepam • Alprazolam • Buspirone

Category	Medication
Strong CYP3A inhibitors	
 • Amiodarone • Cimetidine • Clarithromycin • Diltiazem • Erythromycin • Fluvoxamine • Grapefruit juice • Itraconazole • Ketoconazole • Mibefradil • Nefazodone • Troleandomycin • Verapamil
CYP3A inducers	
 • Carbamazepine • St. John's Wort • Phenobarbital • Troglitazone • Phenytoin • Rifabutin • Rifampin
Hypnotics	Melatonin(prescribed or OTC)
Herbal preparations with sedating effects	-
MAOIs	-
Opioid Analgesics	-
Muscle relaxants (centrally-acting) with known sedating effects	
 • GABA analogues • Hydantoins • Phenyltriazines
Stimulants	
 • Amphetamines • Modafinil • Armodafinil • Methylfenidate • Theophylline
Other	
 • Warfarin, heparin, ticlopidine

Category	Medication
	
• Non-stimulant diet pills• Systemic isotretinoin• Systemic glucocorticoids• Tryptophan

PROTOCOL SIGNATURE PAGE

Study Protocol Number: E2006-A001-102

Study Protocol Title: A Randomized, Double-Blind, Placebo-Controlled, Crossover Study to Evaluate the Respiratory Safety of Lemborexant in Adult and Elderly Healthy Subjects and Adult and Elderly Subjects with Mild Obstructive Sleep Apnea

Investigational Product Name: E2006/Lemborexant

SIGNATURES	
Authors:	
<hr/> 
PPD [Redacted] PPD [Redacted] [Redacted] Neuroscience Business Group Eisai Inc.
	Date
<hr/> 
PPD [Redacted] PPD [Redacted] [Redacted] Neuroscience Business Group Eisai Inc.
	Date

3 INTRODUCTION

The purpose of this statistical analysis plan (SAP) is to describe the procedures and the statistical methods that will be used to analyze and report results for Eisai Protocol E2006-G000-102 (for both cohort 1 and cohort 2). Cohort 1 comprises the healthy volunteer subjects (HV) and cohort 2 comprises the subjects with obstructive sleep apnea (OSA). Additional exploratory or post-hoc analyses not identified in this SAP may be performed to facilitate interpretation of study results and documented in the clinical study report.

This document is prepared on the basis of the final study protocol version 8.0 (dated 11 Dec 2017). The reader is referred to the study protocol, the case report form (CRF), general CRF completion guidelines, and various data collection instruments employed in the study for details of study design, conduct, and data collection.

This SAP is to be reviewed and approved prior to study database lock. If any updates are made upon blinded review of study data or for any other reasons in the course of the study, such modifications and rationale are likewise to be documented and approved prior to unblinding of study database.

3.1 Study Objectives

3.1.1 Primary Objectives

Primary Objective (Healthy Volunteer [HV] Cohort)

To determine whether lemborexant decreases the peripheral oxygen saturation (SpO₂) during total sleep time (TST) in healthy adult and elderly subjects after a single dose of treatment compared with placebo

Primary Objective (Obstructive Sleep Apnea [OSA] Cohort)

To determine whether lemborexant increases the AHI after multiple doses of treatment in adult and elderly subjects with mild OSA compared with placebo

3.1.2 Secondary Objectives

Secondary Objectives (HV Cohort)

1. Determine whether lemborexant increases the apnea-hypopnea index (AHI) after a single dose of treatment compared with placebo
2. Determine whether lemborexant decreases SpO₂ during TST below defined thresholds after a single dose of treatment compared with placebo
3. Evaluate safety and tolerability of lemborexant

Secondary Objectives (OSA Cohort)

1. Determine whether lemborexant increases the AHI after the first dose of treatment compared with placebo
2. Determine whether lemborexant decreases the mean SpO₂ during TST after the first and multiple doses of treatment compared with placebo

3. Determine whether lemborexant increases the proportion of TST during which the SpO₂ is decreased below defined thresholds after the first and multiple doses of treatment compared with placebo
4. Evaluate safety and tolerability of lemborexant

3.1.3 Exploratory Objectives (HV and OSA Cohorts)

Explore the effects of lemborexant compared with placebo after a single dose in HV Cohort and after the first and multiple doses in the OSA Cohort on the following:

5. The mean SpO₂ during rapid eye movement (REM) sleep, non-REM (NREM) sleep, and wake
6. AHI during REM and NREM sleep
7. AHI separately for adult and elderly subjects
8. The mean SpO₂ during TST separately for adult and elderly subjects

In addition, explore the following for both HV and OSA Cohorts:

1. Plasma concentrations of lemborexant and metabolites M4, M9 and M10.
2. Exposure-response (E-R) relationships between lemborexant concentrations and pharmacodynamic (PD) variables, including but not limited to respiratory safety variables (AHI, mean SpO₂ during TST, proportion of TST during which the SpO₂ is decreased below defined thresholds)

3.2 Overall Study Design and Plan

HV Cohort

The HV Cohort comprises a randomized, double-blind, placebo-controlled, 3-period crossover study. Eligible healthy adult and elderly subjects will be randomized to treatment sequence A, B or C, each consisting of 3 Treatment Periods, each of one night's duration, in which subjects will receive a single dose of lemborexant 10 mg, or lemborexant 25 mg, or placebo; Treatment Periods will be separated by a washout interval of at least 14 days. A sufficient number of subjects will be randomized to ensure that 8 evaluable adult subjects (<65 years) and 4 evaluable elderly subjects (≥65 years) complete the study.

Treatment Sequence	Treatment Periods in the HV Cohort		
	1 (one night)	2 (one night)	3 (one night)
A	lemborexant-matched placebo	lemborexant 10 mg	lemborexant 25 mg
B	lemborexant 10 mg	lemborexant 25 mg	lemborexant-matched placebo
C	lemborexant 25 mg	lemborexant-matched placebo	lemborexant 10 mg

OSA Cohort

The OSA Cohort comprises a randomized, double-blind, placebo-controlled, 2-period crossover study.

Adult and elderly subjects with mild OSA will be randomized to treatment sequences D or E, each consisting of 2 Treatment Periods, each of 8 nights' duration, in which subjects will receive lemborexant 10 mg or placebo. The Treatment Periods will be separated by a washout interval of at least 14 days. A sufficient number of subjects will be randomized to ensure that 20 evaluable adult subjects (<65 years) and 10 evaluable elderly subjects (≥ 65 years) complete the study.

Treatment Sequence	Treatment Periods in the OSA Cohort	
	1 (eight nights)	2 (eight nights)
D	lemborexant-matched placebo	lemborexant 10 mg
E	lemborexant 10 mg	lemborexant-matched placebo

Phases of the Study (HV and OSA Cohorts)

For both the HV and OSA cohorts, there will be 2 phases, Prerandomization and Randomization. The Prerandomization Phase for both cohorts will consist of the Screening Period (up to 21 days) and a Baseline Period (≤ 1 day prior to randomization).

For the HV Cohort, the Randomization Phase will comprise 3 Treatment Periods, each of 1-day duration, separated by a washout interval of at least 14 days, followed by a 14-day Follow-Up Period.

For the OSA Cohort, the Randomization Phase will comprise 2 Treatment Periods, each of 8 days duration, separated by a washout interval of at least 14 days, and a Follow-Up Period of 14 days.

For both cohorts, an End of Study (EOS) Visit will occur at least 14 days after the final dose of study medication.

4 DETERMINATION OF SAMPLE SIZE

Sample Size Rationale

HV Cohort:

A mean difference of 5 percentage points between treatments in SpO₂ is considered to be clinically meaningful in a study of the respiratory safety of suvorexant in healthy adult volunteers (Uemura, et al., 2015). From that source, the within-subject variance is assumed to be 0.315%. With a total of 12 subjects (4 elderly and 8 adults) completing the study and assuming that the true difference between treatments is -1.0, there is 99% power that the lower bound of the 90% confidence interval for the difference in SpO₂ (lomborexant - placebo) would be greater than -5. Although the estimate of within-subject variability is based on a study of adult healthy volunteers, the addition of elderly subjects is expected to have a minimal effect on the combined variability and thus a minimal effect on the power.

OSA Cohort: A mean difference between treatments in AHI > 5 is considered clinically meaningful in studies of the respiratory safety of sleep agents in OSA (Kryger, et al., 2007, Sun, et al., 2016). The within-subject variance is assumed to be 25.34 for AHI for adult subjects (Sun, et al, 2016) and 30.41 for AHI for elderly subjects (where the elderly within-subject variance is estimated from adult data + 20%, Mitterling, et al, 2015; Lee, et al, 2016). Assuming the true difference in AHI (lomborexant – placebo) on Day 8 is as high as 1.5, a total of 30 subjects completing the study (20 adult, 10 elderly), provides 82% power that the upper bound of the 90% CI for the treatment difference in AHI (lomborexant – placebo) on Day 8 would be < 5.

Sample Size Estimates for OSA Cohort

Description	Combined within-subject variance of AHI	Adult N	Elderly N	Total N	Total Power (%)
80% overall power with 20 adult subjects	26.96	20	10	30	82
85% overall power with 20 adult subjects	27.38	20	14	34	86
80% overall power with 20 elderly subjects	28.54	12	20	32	82
85% overall power with 20 elderly subjects	28.16	16	20	36	86
Equal number of subjects	27.875	20	20	40	90

5 STATISTICAL METHODS

All analysis will be reported separately for each cohort. All descriptive statistics for continuous variables will be reported using mean, standard deviation (SD), median, minimum and maximum. Categorical variables will be summarized as number (percentage) of subjects.

All statistical tests will be based on the 5% level of significance (2-sided), unless otherwise stated. If statistical comparisons are not defined, all pairwise comparisons will be tested.

5.1 Study Endpoints

5.1.1 Primary Endpoints

Primary Endpoint (HV Cohort)

The mean SpO₂ during TST on Day 1 of treatment

Primary Endpoint (OSA Cohort)

The AHI on Day 8 of treatment

5.1.2 Secondary Endpoints

Secondary Endpoints (HV Cohort)

1. The AHI on Day 1 of treatment
2. The percentage of TST during which SpO₂ is <90%, <85% and <80% on Day 1 of treatment
3. The proportion of subjects with at least one incident of SpO₂ <90% for at least 30 seconds during TST on Day 1 of treatment

Secondary Endpoints (OSA Cohorts)

1. The AHI on Day 1 of treatment
2. The mean SpO₂ during TST on Day 1 and Day 8 of treatment
3. The percentage of TST during which the SpO₂ is <90%, <85% and <80% on Day 1 and Day 8 of treatment
4. The proportion of subjects with at least one incident of SpO₂ <90% for at least 30 seconds during TST on Day 1 and Day 8 of treatment.

Exploratory Endpoints (HV and OSA Cohorts)

1. The mean SpO₂ during REM sleep, NREM and wake
2. The AHI during REM and NREM sleep
3. The AHI separately for adult and elderly subjects at all days assessed
4. The mean SpO₂ during TST separately for adult and elderly subjects at all days assessed

Pharmacokinetic Endpoint (HV and OSA Cohorts)

Lemborexant and metabolites M4, M9 and M10 plasma concentrations

Pharmacokinetic/Pharmacodynamic (Exposure-Response) Endpoint (HV and OSA Cohorts)

Correlations between plasma concentrations of lemborexant and select pharmacodynamic variables including AHI, mean SpO₂ during TST, and proportion of TST in which SpO₂ is <90%, <85% and <80% at all days assessed.

5.2 Study Subjects

5.2.1 Definitions of Analysis Sets

Analyses defined below are for each cohort separately.

Safety Analysis Set: Group of subjects who received study drug and have at least one postdose safety assessment.

Pharmacodynamic Analysis Set: The PD Analysis Set is the group of subjects who received at least 1 dose of study drug in each Treatment Period and who had sufficient PD data to derive at least 1 primary PD parameter.

Pharmacokinetic Analysis Set: Group of subjects who received at least 1 dose of lemborexant and who had sufficient PK data to derive at least 1 PK parameter.

5.2.2 Subject Disposition

The number of subjects screened and the number failing screening for each cohort (overall and by reason for failure) will be summarized. Screen failure data will be listed by cohort. The number of subjects randomized along with the number of subjects in each of the study populations will also be presented.

All disposition tables will be presented by cohort as follows:

The number of subjects completing the study will be presented. Subjects who prematurely terminated their participation in the study will be summarized by their primary reason for study termination. Other reasons for study drug and study terminations will also be summarized. These tabulations will be produced for all randomized subjects by treatment sequence.

The number of subjects screened and the number failing screening (overall and by reason for failure) will be summarized. Screen failure data will be listed. The number of subjects randomized along with the number of subjects in each of the study populations will also be presented.

The number of subjects completing the study will be presented. Subjects who prematurely terminated their participation in the study will be summarized by their primary reason for study termination. Other reasons for study drug and study terminations will also be summarized. These tabulations will be produced for all randomized subjects by treatment sequence.

The number and percentage of subjects will be summarized with the number in the FAS as the denominator, together with the number of subjects randomized but never dosed:

- Randomized but never dosed (only showing number of subjects)

- Completed treatment
- Prematurely discontinued treatment and the reasons for discontinuations
- Completed study
- Prematurely discontinued the study and the reasons for discontinuations

A listing will be provided for subjects who discontinued treatment or who discontinued study with reasons for discontinuation. A randomization listing will be provided with subjects ordered by randomization date.

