9.1.2.2.1 TREATMENT PERIODS (OSA COHORT)

Subjects who continue to meet the eligibility criteria will be randomized in treatment sequences D or E consisting of 2 Treatment Periods, 8 nights duration each: lemborexant 10 mg and placebo, with the treatments periods separated by a washout interval of at least 14 days. Randomization will be stratified by age (<65 years vs ≥65 years). Within each age stratum, subjects will be randomized to 1 of the 2 treatment sequences in a 1:1 ratio.

Treatment Period 1

Subjects will remain overnight in the sleep laboratory. Subjects will undergo the following procedures at the Screening Visits 1 and 2 and on Day 1: urine pregnancy test for female subjects of childbearing potential, and for all subjects, a urine drug test and breath alcohol

test). Bedtime (lights off) will be at the MHB that was used at the second Screening Visit (Visit 2). Subjects will receive study drug immediately (within 5 minutes) before lights off. The PSG recording will begin at lights off and will continue for 8 hours (until lights on). The following morning, a PK blood sample will be collected and vital signs assessed, as indicated in the Schedule of Procedures/Assessments. Subjects will be provided with study drug to be administered for 6 consecutive nights at home, and will be instructed to take the medication immediately (within 5 minutes) of bedtime. Subjects will also be instructed on study restrictions related to prohibited medications/drugs, caffeine and alcohol, and the prohibitions regarding the use of CPAP device or dental appliance. If SpO₂ <80% for ≥ 20% of TST during the first night of treatment, the subject must be early terminated. Subjects may leave the clinic after the investigator determines that it is safe for them to do so. Subjects will be instructed to promptly contact investigator in case of any new complaints or exacerbation of current symptoms.

On Day 5 (with a window of ±2 days), the site will telephone the subject to assess AEs and record concomitant medications. If any AE is suspected as significant and requires a clinic visit, an Unscheduled Visit should be conducted as soon as possible.

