9.5.1.5.1 ADVERSE EVENTS AND EVENTS ASSOCIATED WITH SPECIAL SITUATIONS

An adverse event (AE) is any untoward medical occurrence in a patient or clinical investigation subject administered an investigational product. An AE does not necessarily have a causal relationship with the medicinal product. For this study, the study drug(s) is lemborexant.

The criteria for identifying AEs in this study are:

- Any unfavorable and unintended sign (including an abnormal laboratory finding), symptom, or disease temporally associated with the use of an investigational product, whether or not considered related to the investigational product (Note: Every sign or symptom should not be listed as a separate AE if the applicable disease [diagnosis] is being reported as an AE)
- Any new disease or exacerbation of an existing disease
- Any deterioration in nonprotocol-required measurements of a laboratory value or other clinical test (eg, ECG or x-ray) that results in symptoms, a change in treatment, or discontinuation of study drug
- Recurrence of an intermittent medical condition (eg, headache) not present pretreatment (Baseline)
- An abnormal laboratory test result should be considered an AE if the identified laboratory abnormality leads to any type of intervention, withdrawal of study drug, or withholding of study drug, whether prescribed in the protocol or not.

All AEs observed during the study will be reported on the CRF. All AEs, regardless of relationship to study drug or procedure, should be collected beginning from the time the subject signs the study ICF through the last visit. Subjects who fail screening primarily due to AE(s) must have the AE(s) leading to screen failure reported on the Screening Disposition CRF. Serious AEs will be collected for 28 days after the last dose

Abnormal laboratory values should not be listed as separate AEs if they are considered to be part of the clinical syndrome that is being reported as an AE. It is the responsibility of the investigator to review all laboratory findings in all subjects and determine if they constitute an AE. Medical and scientific judgment should be exercised in deciding whether an isolated

laboratory abnormality should be classified as an AE. Any laboratory abnormality considered to constitute an AE should be reported on the Adverse Event CRF.

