9.5.5 Completion/Discontinuation of Subjects

The investigator may withdraw the subject from the study at any time for safety or administrative reasons. A subject may elect to discontinue the study at any time for any reason. All subjects who discontinue the study are to complete the study's early discontinuation procedures indicated in the Schedule of Procedures/Assessments ([Table 5](#) and [Table 6](#)).

The investigator will promptly explain to the subject involved that the study will be discontinued for that subject and provide appropriate medical treatment and other necessary measures for the subject. A subject who has ceased to return for visits will be followed up by mail, phone, or other means to gather information such as the reason for failure to return, the

status of treatment compliance, the presence or absence of AEs, and clinical courses of signs and symptoms.

Subjects who discontinue early from the study will be discontinued for 1 of these primary reasons: AE(s), lost to follow-up, subject choice, withdrawal of consent or other. In addition to the primary reason, the subject may indicate 1 or more of secondary reasons for discontinuation. Study disposition information will be collected on the Subject Disposition CRF.

A subject removed from the study for any reason will be replaced.

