9.7.1.3 Subject Disposition

The number of subjects screened and the number failing screening (overall and by reason for failure) will be summarized. Screen failure data will be listed. The number of subjects randomized along with the number of subjects in each of the study populations will also be presented.

The number of subjects completing the study will be presented. Subjects who prematurely terminated their participation in the study will be summarized by their primary reason for study termination. Other reasons for study drug and study terminations will also be summarized. These tabulations will be produced for all randomized subjects by treatment.

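### SAP 5.2.2 tabulates withdrawals by treatment sequence where the protocol says by treatment, so withdrawals not recorded as adverse events get no drug-versus-placebo table

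*SAP*

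**What the plan says.** On grouping, the two documents differ. Protocol 9.7.1.3, on completion, premature termination and reasons: "These tabulations will be produced for all randomized subjects by treatment". SAP 5.2.2 carries the same text over, twice, but ends it differently: "These tabulations will be produced for all randomized subjects by treatment sequence". SAP section 7, on changes to the planned analyses, says not applicable.

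On the denominator, a later part of SAP 5.2.2 introduces a list of completed and discontinued categories with this sentence: "The number and percentage of subjects will be summarized with the number in the FAS as the denominator". No grouping is stated for that list. FAS is expanded in the SAP's abbreviation list, but SAP 5.2.1 defines only the Safety, PD and PK sets.

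On the OSA desaturation rule, protocol 9.1.2.2.1 provides that if SpO2 is below 80% for at least 20% of TST "during the first night of treatment, the subject must be early terminated". The synopsis has the same rule. The primary reasons for discontinuation in protocol 9.5.5 are "AE(s), lost to follow-up, subject choice, withdrawal of consent or other". One of the adverse-event criteria in protocol 9.5.1.5.1 reads "Any deterioration in nonprotocol-required measurements of a laboratory value or other clinical test".

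SAP 5.6.1 gives a TEAE overview by treatment group that includes TEAEs leading to discontinuation, and a table of those TEAEs by SOC and PT for each treatment. SAP 5.2.2 also plans a listing of discontinued subjects with reasons.

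**The concern.** In a crossover, each subject is randomized to an order of treatments, and each order here includes every treatment in its cohort. A sequence column therefore adds withdrawals on lemborexant to withdrawals on placebo. The protocol's by-treatment column answers the tolerability question (do more subjects stop on drug?), which falls under the safety and tolerability objective of each cohort. The SAP's column does not, and the change is not declared.

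What is at stake is the set of withdrawals that reach no adverse-event table. The one most relevant to a respiratory-safety trial is a termination forced by the SpO2 rule. It has no reason category, so unless it is recorded as an AE it may be entered as *other*, and the only summary that counts it would then be a sequence table.

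**Working it through.** The documents give no withdrawal rates, so there is no stated figure to reproduce. The rates below are assumptions, varied over a range. The 15 subjects per OSA sequence come from the planned 30 split by 1:1 allocation, ignoring replacements.

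**Step 1. What a sequence column shows.** Let pL and pP be the probabilities of withdrawing in a period on lemborexant and on placebo. A withdrawn subject does not enter the next period, and there is no period effect.

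- Sequence D (placebo, then lemborexant): 1 − (1 − pP)(1 − pL)
- Sequence E (lemborexant, then placebo): 1 − (1 − pL)(1 − pP)

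The two expressions are identical whatever pL and pP are.

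**Step 2. What a treatment column shows.** Withdrawals on lemborexant are 15(1 − pP)pL + 15pL, out of 15(1 − pP) + 15 dosed. Withdrawals on placebo are 15pP + 15(1 − pL)pP, out of 15 + 15(1 − pL) dosed.

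| Assumed pL, pP | D vs E | Lemborexant | Placebo |
|---|---|---|---|
| 10%, 2% | 11.8% vs 11.8% | 2.97 of 29.7 (10%) | 0.57 of 28.5 (2%) |
| 20%, 5% | 24% vs 24% | 5.85 of 29.25 (20%) | 1.35 of 27.0 (5%) |
| 30%, 0% | 30% vs 30% | 9.0 of 30 (30%) | 0 of 25.5 (0%) |

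For the HV cohort, with assumed risks of 20% on 25 mg, 5% on 10 mg and 0% on placebo, sequences A, B and C each show 1 − 0.80 × 0.95 × 1.00 = 24%.

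**Step 3. A count example.** Suppose four OSA subjects withdraw on lemborexant and none on placebo, two in D (Period 2) and two in E (Period 1). By sequence this is 2/15 vs 2/15. By treatment it is 4/30 vs 0/28, the placebo denominator being 15 in D plus 15 − 2 = 13 in E.

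**Step 4. When cancellation fails.** Keep pL = 20% and pP = 5% in Period 1 and apply an assumed odds ratio to Period 2. With 0.5, D and E show 15.6% and 22.1%. With 2, they show 36.7% and 27.6%. The sign of the D–E difference reverses although the treatment effect on the odds scale is unchanged, so that difference does not estimate the treatment effect. At the other extreme, if all withdrawals fall in Period 1, sequence and treatment coincide and the sequence table does show the contrast.

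**Step 5. Where an OSA desaturation termination appears.**

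| Route | By-treatment summary |
|---|---|
| Recorded as a TEAE leading to discontinuation, either period | Yes, SAP 5.6.1 |
| Not an AE, Period 2 | No withdrawal table. The subject was dosed in both periods and can enter the PD set, so the night can contribute to the Day 1 percentage of TST with SpO2 below 80% |
| Not an AE, Period 1 | None. SAP 5.2.1 requires a dose in each Treatment Period, so the subject is outside the PD set. What remains is the sequence table and the listing |

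Vital-sign SpO2 does not fill the gap: the notes to protocol Table 6 say it is recorded at Screening Visit 1 only. The Period 2 row assumes the rule also applies on the first night of Period 2, because protocol 9.1.2.2.1 says Period 2 follows the same procedures.

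**The case against.** The strongest reply is that this is largely a documentation mismatch. Subjects are randomized to sequences, so sequence is a natural column for a disposition table of everyone randomized, and the protocol leaves analysis details to the SAP. Several specific objections stand:

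- A reader might infer that a lemborexant excess of withdrawals vanishes from all the tables. It does not: SAP 5.6.1 shows AE-led discontinuations by treatment in two places.
- A reader might infer that desaturation terminations are, by design, not adverse events, because the clinical-test criterion is limited to measurements the protocol does not require and PSG oximetry is required. That criterion is one of several alternatives. Another covers any unfavorable and unintended sign, and another the worsening of an existing disease. The documents leave AE status open.
- A reader might combine the sentences of SAP 5.2.2 into a table by sequence over the FAS. No such table is specified. The by-sequence tables are for all randomized subjects, and the FAS list has no stated grouping.
- Cancellation holds in expectation, under equal allocation and no period effect. The count example is symmetric by construction.
- Few such terminations may occur, because OSA subjects with SpO2 below 80% for 5% or more of TST at screening are excluded, while the rule needs 20%.
- The discontinuation and randomization listings may allow reconstruction.

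What the reply does not answer is that the protocol did specify by treatment, the SAP changed it without saying so, and the new column cannot show the contrast. The listing is not said to carry treatment or period at withdrawal, and a listing is not a summary. The PD-set exclusion of Period 1 terminations is a separate feature of the plan. Changing the disposition columns does not repair it, which is why the fix counts the criterion directly in the Safety Analysis Set.

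**Conclusion.** The point holds in a limited form. SAP 5.2.2 departs from protocol 9.7.1.3 without declaring it, and its sequence tables cannot be read for a treatment difference in withdrawals. Under the assumed risks of 20% and 5%, a 15-point difference appears as 24% in both OSA sequences. The loss concerns withdrawals not recorded as TEAEs. It is sharpest for an OSA termination under the SpO2 rule in Period 1 that is not recorded as an AE, because no planned summary described in the SAP would then show it by treatment. How many such cases would arise cannot be judged from the documents. The table shells are in a separate document, so any by-treatment column there could not be checked.

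The undefined FAS is a separate and smaller defect: SAP 5.2.2 uses two denominators, one of which has no membership rule.

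None of this touches a primary estimate, interval or decision rule. It concerns the safety and tolerability objective, and it is worth correcting because the correction is cheap.

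**What to change.** In SAP 5.2.2:

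- Add a table of discontinuations and primary reasons by treatment at discontinuation, with subjects dosed with that treatment as the denominator. Assign a withdrawal during washout to the treatment of the preceding period. Keep the sequence table.
- Replace FAS with a defined set. The nearest one already in SAP 5.2.1 is: "Safety Analysis Set: Group of subjects who received study drug and have at least one postdose safety assessment". State which percentages use it and which use all randomized subjects.

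With the respiratory safety results, report n (%) of OSA subjects who met the protocol's existing SpO2 discontinuation criterion, by treatment, in the Safety Analysis Set. Derive it from the PSG oximetry and count it whatever the AE coding. A separate reason code on the Subject Disposition CRF would help but is optional.

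Record the difference from protocol 9.7.1.3 in SAP section 7. The by-treatment denominator proposed here also differs from the protocol's all-randomized one, so it belongs in the same note.

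The cost is one or two extra tables and a washout attribution convention. No new measurements are needed, and the clinical threshold and rule stay as they are.
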